Appendix 2: Surgical flowcharts

A. Surgery of the ipsilateral groin in case a tumour is situated > 1 cm from the midline

Any SLN showing on the scintigram in the *contralateral* groin is removed, regardless previous treatment. When the SLN fails, further treatment is not warranted.

In the middle previous treatment of the *ipsilateral* groin.

At the right hand site treatment of *ipsilateral* groin.

[figure not shown]

Figure 5 Surgery of the ipsilateral groin in case a tumour is situated > 1 cm from the midline

B Surgery in case a tumour is within 1 cm from the midline, without crossing the midline

Any SLN showing on the scintigram in the *contralateral* groin is removed, regardless previous treatment.

In the middle previous treatment of the groins

At the right hand site treatment of ipsilateral groin.

Green boxes to be discussed with the patients and decision documented in the chart

[figure not shown]

Figure 6 Surgery in case a tumour is within 1 cm from the midline, without crossing the midline

C Surgery in case a tumour crosses the midline

The schedule applies for both groins.

In the middle previous treatment per groin.

At the right hand site treatment per groin.

(*) in case of previous bilateral IFL with radiotherapy the patients should be consented for the non- SLN cohort study.

[figure not shown]

Figure 7 Surgery in case a tumour crosses the midline

Appendix 3: CTCAE criteria

Common Terminology Criteria for Adverse Events (CTCAE) Version 4.0 Published: May 28, 2009 (v4.03: June 14, 2010) (https://evs.nci.nih.gov/ftp1/CTCAE/CTCAE_4.03_2010-06-14_QuickReference_5x7.pdf)

	Grade				
Adverse Event	1	2	3	4	5
Infections and infestations					
Urinary tract infection Definition: A disorder characterized by an infectious process involving the urinary tract, most commonly the urethra and bladder.	-	Localized: local intervention indicated (e.g., topical antibiotics, antifungal or antiviral)	IV antibiotics, antifungal or antiviral intervention indicated; radiologic or operative intervention indicated	Life-threatening consequence: urgent intervention indicated	Death
Skin infection Definition: A disorder characterized by an infectious process involving the skin	Localized, local intervention indicated	Oral intervention indicated (e.g., antibiotic, antifungal, antiviral)	IV antibiotic, antifungal, or antiviral intervention indicated; radiologic or operative intervention indicated	Life-threatening consequence: urgent intervention indicated	Death
Wound infection: Definition: A disorder characterized by an infectious process involving the wound.	-	Localized; local intervention indicated (e.g., topical antibiotic, antifungal, or antiviral)	IV antibiotic, antifungal, or antiviral intervention indicated; radiologic or operative intervention indicated	Life-threatening consequence: urgent intervention indicated	Death
Vascular disorders					
Lymphedema Definition: A disorder characterized by excessive fluid	Trace thickening or faint discoloration	Marked discoloration; leathery skin texture; papillary formation;	Severe symptoms; limiting self care ADL		

collection in tissues that causes swelling		limiting instrumental ADL			
Lymphocele Definition: A disorder characterized by a cystic lesion containing lymph	Asymptomatic; clinical or diagnostic observations only; intervention not indicated	Symptomatic; medical intervention indicated	Severe symptoms; radiologic, endoscopic or elective operative intervention indicated		

Appendix 4: Procedures and forms data collection.

Patient's registration will only be accepted from authorized investigators.

Patients should sign informed consent prior to registry.

Overview of the forms and additional documents to be collected:

Form	Name	When	Additional documents
A	ELIGIBILITY FORM (A)	Registration	
B	DECISION ON TREATMENT FORM (B)	Registration	
C	PRIMARY TUMOUR & LYMPH NODES FORM (C)		Photograph when (still) available
D1	CURRENT TUMOUR & LYMPH NODES FORM (D1)		Photograph with ruler
D2	PRE OPERATIVE IMAGING FORM-ULTRASOUND- (D2)		Copy of imaging report CoIR)
D3	PRE OPERATIVE IMAGING FORM-CT- (D3)		CoIR
D4	PREOPERATIVE IMAGING FORM –MRI- (D4)		CoIR
E	TUMOUR SURGERY TREATMENT FORM (E)		Surgical notes
F	SENTINEL NODES SURGERY FORM (F)		Surgical notes
G	POSTOPERATIVE PERIOD FORM (G)		
H	PATHOLOGY REPORT FORM (H)	After surgery	Original pathology report
J	ADDITIONAL TREATMENT FORM (J)		
K	FOLLOW UP FORM 3 MONTHS AFTER COMPLETION OF TREATMENT(k)		
L	FOLLOW UP FORM 6 MONTHS AFTER COMPLETION OF TREATMENT: clinical assessment (L)		
M	FOLLOW UP FORM 6 MONTHS AFTER COMPLETION OF TREATMENT: Ultrasound scan(M)	6m	CoIR
N	FOLLOW UP FORM 9 MONTHS AFTER COMPLETION OF TREATMENT(N)		
O	FOLLOW UP FORM 12 MONTH AFTER COMPLETION OF TREATMENT clinical assessment(O)		
P	FOLLOW UP FORM 12 MONTHS AFTER COMPLETION OF TREATMENT ultrasound scan (P)	12 m	CoIR

Q	FOLLOW UP FORM 15 MONTHS AFTER COMPLETION OF TREATMENT(Q)		
R	FOLLOW UP FORM 18 MONTHS AFTER COMPLETION OF TREATMENT(R)		
S	FOLLOW UP FORM 21 MONTHS AFTER COMPLETION OF TREATMENT(S)		
T	FOLLOW UP FORM 24 MONTHS AFTER COMPLETION OF TREATMENT(T)	24 m	

Patients must be registered prior to surgery. A patient can be registered after verification of eligibility: Form A (eligibility form).

At registration, before surgery Form B (planned surgery) should be completed to minimize bias.

At the end of the registration procedure, a number will be allocated to the patient (patient sequential study number) send by the study secretariat by fax or email.

The study identification number attributed to the patient at the end of the registration procedure identifies the patient and must be reported on all case forms.

After surgery additional treatment is given, or the observational study starts.

Patient data will be collected in standard case report forms with NCR (non-carbon required) paper or through an electronic database.

Patient data are only available to the principal investigators at each participating institution. CRFs must be completed and signed by the investigator as soon as the requested information is available, according to the schedule (see below). It is the responsibility of the investigator to check that all original CRFs have been sent to the Study secretariat and that they are completely and correctly filled out. The original CRF papers must be sent to the study secretary, the copies of the NCR papers remain in the study centre.

Data, as collected in the CRF will be sent to the study-secretary

V2SLN studie, [name]

Erasmus MC Cancer Institute

Department of Gynaecological Oncology

[name]

[name]

[name]

Email: [contact]

CRFs must be completed according to the following schedule:

1. Registration: Before treatment starts send eligibility form (A) and decision on treatment Form (B) to the study secretariat The study secretariat will return a patient sequential identification number.
2. After completion of surgical treatment Form C-H, an image of the tumour, with a cm marker, and the corresponding copies of the Pathology Report(s) copies, imaging reports and surgical notes.
3. In case of additional treatment Forms J as soon as possible, but no later than at 6 months.
4. At 6 months after treatment Form J – M.
5. At 12 months after treatment Form N – P.
6. At 24 months after treatment Form Q - T.

When a groin recurrence, or death occurs and has been confirmed by pathology, the study coordinator and/or study secretary will be notified immediately. The study coordinator will determine whether the stopping rule has to be activated.

Appendix 6: Questionnaires

	EQ-5D-5L. baseline. 6 and 12 months	Adjusted GCLQ baseline, 6 and 12 months	Decisional Conflict Scale (DCS). baseline.	Decision Regret Scale (DRS). 1 year after surgery.
Non- SLN cohort	X	X		
V2SLN Group A	X	X	X	X
V2SLN Group B1	X	X	X	X
V2SLN Group B2	X	X	X	X
V2SLN Group C	X	X	X	X

EQ-5D-5L

Zet bij iedere groep in de lijst hieronder een kruisje in het hokje achter de zin die het best past bij uw eigen gezondheidstoestand vandaag.

Mobiliteit

Ik heb geen problemen met lopen

Ik heb enige problemen met lopen

Ik ben bedlegerig

Zelfzorg

Ik heb geen problemen om mijzelf te wassen of aan te kleden

Ik heb enige problemen om mijzelf te wassen of aan te kleden

Ik ben niet in staat mijzelf te wassen of aan te kleden

Dagelijkse activiteiten (bijv. werk, studie, huishouden, gezins- en vrijetijdsactiviteiten)

Ik heb geen problemen met mijn dagelijkse activiteiten

Ik heb enige problemen met mijn dagelijkse activiteiten

Ik ben niet in staat mijn dagelijkse activiteiten uit te voeren

Pijn/klachten

Ik heb geen pijn of andere klachten

Ik heb matige pijn of andere klachten

Ik heb zeer ernstige pijn of andere klachten

Stemming

Ik ben niet angstig of somber

Ik ben matig angstig of somber

Ik ben erg angstig of somber

Adjusted GCLQ

Please check one answer per line.

- | | |
|--|--|
| 1. Do you have limited movement of your knee? | Yes  No  |
| 8. Have you experienced swelling of your foot, leg, hip, groin or your lower body in the past 4 weeks? | Yes  No  |
| 10. Have you experienced redness of your foot, leg, hip, groin or your lower body in the past 4 weeks? | Yes  No  |
| 12. Have you experienced firmness/tightness? | Yes  No  |
| 14. Have you experienced heaviness of the legs? | Yes  No  |
| 17. Have you experienced aching in de benen? | Yes  No  |
| 19. Have you experienced groin swelling? (genital, labia/vulvar) | Yes  No  |

In Nederlands:

De volgende vragen hebben betrekking op klachten die u zou kunnen hebben van uw voeten, benen, heup, lies of onderlichaam in de afgelopen 4 weken:

- | | |
|--|--|
| Had u last van zwelling van de weefsels in het genoemde gebied? | Ja  Nee  |
| Had u last van roodheid in het genoemde gebied? | Ja  Nee  |
| Had u last van een gespannen beklemmend of vast gevoel in het genoemde gebied? | Ja  Nee  |
| Had u pijn in het genoemde gebied? | Ja  Nee  |
| Had u last van een zwaar gevoel in de benen? | Ja  Nee  |
| Had u last van een zwelling van uw lies, en of in de schaamstreek? | Ja  Nee  |
| Had u last van verminderde bewegelijkheid van uw knie? | Ja  Nee  |

Decision Conflict Scale

De volgende stellingen gaan over de beslissing die u hebt gemaakt over welke operatie u zal ondergaan. Kunt u aangeven in hoeverre u het eens bent met deze stellingen? De antwoorden worden gegeven op een 5-punts schaal van helemaal mee eens tot helemaal mee oneens.

	Onzekerheid over de beslissing
1.	Ik vind/vond het moeilijk om deze beslissing te nemen Helemaal mee eens      Helemaal mee oneens
2.	Ik weet/wist niet zeker wat ik moet beslissen Helemaal mee eens      Helemaal mee oneens
3.	Het is/was duidelijk wat voor mij de beste keuze is Helemaal mee eens      Helemaal mee oneens
	Factoren die bijdragen aan de onzekerheid
4.	Ik ben/was mij bewust van de keuze die ik moe(s)t maken tussen de verschillende opties Helemaal mee eens      Helemaal mee oneens
5.	Ik heb/had het gevoel dat ik op de hoogte ben van de voordelen van de innovatieve (nieuwe) preventieve strategie Helemaal mee eens      Helemaal mee oneens
6.	Ik heb/had het gevoel dat ik op de hoogte ben van de voordelen van beide opties Helemaal mee eens      Helemaal mee oneens
7.	Ik heb/had het gevoel dat ik op de hoogte ben van de nadelen (risico's en bijwerkingen) van de huidige standaard preventieve strategie Helemaal mee eens      Helemaal mee oneens
8.	Ik heb/had het gevoel dat ik op de hoogte ben van de nadelen (risico's en bijwerkingen) van de innovatieve (nieuwe) preventieve strategie Helemaal mee eens      Helemaal mee oneens
9.	Ik heb/had meer advies en informatie nodig Helemaal mee eens      Helemaal mee oneens
10.	Ik weet hoe belangrijk de voordelen van elke optie zijn/waren bij het nemen van deze beslissing Helemaal mee eens      Helemaal mee oneens
11.	Ik weet hoe belangrijk de nadelen van elke optie zijn/waren bij het nemen van deze beslissing Helemaal mee eens      Helemaal mee oneens
12.	Het is moeilijk te bepalen of de voordelen belangrijker zijn dan de nadelen of andersom Helemaal mee eens      Helemaal mee oneens
13.	Ik voel(de) me bij het nemen van de beslissing door anderen onder druk gezet Helemaal mee eens      Helemaal mee oneens
14.	Ik krijg/kreeg voldoende steun van anderen bij het maken van deze beslissing Helemaal mee eens      Helemaal mee oneens
	Beantwoord de volgende vragen alleen als u de beslissing al heeft gemaakt
15.	Ik heb/had het gevoel dat ik goed geïnformeerd was toen ik deze beslissing nam Helemaal mee eens      Helemaal mee oneens
16.	Deze beslissing geeft aan wat voor mij belangrijk is/was Helemaal mee eens      Helemaal mee oneens
17.	Ik verwacht dat ik bij mijn beslissing blijf Helemaal mee eens      Helemaal mee oneens

18.	Ik ben tevreden over mijn beslissing Helemaal mee eens      Helemaal mee oneens
-----	--

Decision Regret Scale (DRS).

U bent inmiddels behandeld. De volgende vragen gaan over hoe u achteraf terugkijkt op de keuze die u heeft gemaakt. Geef voor de volgende uitspraken aan in welke mate u het met deze uitspraken eens bent.

	Geheel mee oneens	oneens	Niet oneens, niet eens	eens	Geheel mee eens
1. Het was de juiste keuze					
2. Ik heb spijt van de beslissing die is genomen					
3. Ik zou dezelfde keuze maken als ik het zou moeten overdoen					
4. De keuze heeft mij veel schade gedaan					
5. De beslissing was een wijze beslissing

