8.1.3 Other study parameters

Baseline data:

FIRST procedure: age at first procedure, localisation of tumour (medial / lateral), tumour size, depth of infiltration, LVSI, number of SLN right groin, number of SLN

left groin, IFL right site (number of lymph nodes), IFL left site (number of lymph nodes), previous radiotherapy, presence of LS or dysplasia, previous reconstructive surgery.

Interval between first surgical treatment and moment of relapse, guessed / estimated distance (cm) between original tumour and relapse, localisation of relapsed tumour, tumour size.

Intention to remove SLN ipsi- or bilateral, agreement on performing IFL in case SLN is not detected or retrieved.

Questionnaires

EQ-5D-5L. Standardized descriptive system of health-related quality of life states consisting of five dimensions (mobility, self-care, usual activities, pain/discomfort, anxiety/depression) each of which can take one of five responses. The responses record five levels of severity (no problems/some problems/ moderate problems/severe problems/extreme problems) within a particular EQ-5D dimension. Besides the descriptive system, a standard vertical 20 cm visual analogue scale (similar to a thermometer) for recording an individual's rating for their current health-related quality of life state is part of the EQ-5D. It was developed by the EuroQol Group. (14, 15)

Decisional Conflict Scale (DCS). This scale measures: 1) health-care consumers' uncertainty in making a health-related decision; 2) the factors contributing to the uncertainty; and 3) health-care consumers' perceived effective decision making. Internal consistency coefficients range from 0.78 to 0.92. (16) This questionnaire will only be used at baseline.

Decision Regret Scale (DRS). The DRS is a 5-item scale and a useful indicator of health care decision regret at a given point in time. Internal consistency is good (Cronbach's alpha = 0.81 to 0.92). This questionnaire will be used to evaluate patient's decision 1 year after surgery. (17)

GCLQ7 questionnaire: This is a short version of the Gynaecologic Cancer Lymphedema Questionnaire. This questionnaire will be used at baseline, 6 and 12 months. (18)

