Total number of groins with tumour positive SLNs, divided by the number of groins with successful SLN procedure * 100%.

Tumour positive groins

- in relation to participants / patients with groin surgery (pathology only):

Total number of women with uni or bilateral tumour positive lymph nodes, retrieved either by SLN or by IFL, divided by the number of women that underwent groin surgery * 100% (including women included in the non-SLN cohort, excluding women that did not have groin surgery in groups B2 C).

- in relation to participants / patients with first vulvar cancer recurrence:

Total number of women with uni or bilateral tumour positive lymph nodes, retrieved either by SLN or by IFL, and all women experiencing a groin recurrence during 24 month follow up, divided by the number of women included in the current study * 100% (including women included in the non-SLN cohort, and women that did not have groin surgery in group B2 and C).

- per groin:

Total number of tumour positive nodes divided by the number of groins treated *100%.

Outcome quality of life

QoL measurements will be done at baseline and 6, and 12 months after surgery.

Linear description and comparison between standard treated and study arm treated patients will be performed. (Groups non SLN cohort, and A - C)

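### The form printed under EQ-5D-5L in Appendix 6 has three response levels per dimension, while section 8.1.3 specifies five; the two must be reconciled and the live forms checked

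*Protocol*

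**What the plan says.** Section 8.1.3 (Other study parameters, Questionnaires) names the EQ-5D-5L. It describes five dimensions, "each of which can take one of five responses", and labels the levels "no problems/some problems/ moderate problems/severe problems/extreme problems". It adds "a standard vertical 20 cm visual analogue scale" as part of the instrument.

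The table at the start of Appendix 6 repeats the name and gives the schedule, "EQ-5D-5L. baseline. 6 and 12 months". It marks the instrument for the non-SLN cohort and for groups A, B1, B2 and C.

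The form then printed in Appendix 6 under the heading EQ-5D-5L is in Dutch. Its mobility item reads, in full, "Ik heb geen problemen met lopen", "Ik heb enige problemen met lopen", "Ik ben bedlegerig": no problems walking, some problems walking, confined to bed. The other four items also have three statements each.

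The data feed section 10.2, where "QoL measurements will be done at baseline and 6, and 12 months after surgery" and patients given standard treatment are compared with those in the study arm. The Summary lists quality of life among the secondary endpoints, and secondary objectives 2 and 3 in section 2 both include it. Section 8.3 says that questionnaires are issued centrally by the datacentre as a web link, with paper for participants who cannot use the web version.

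**The concern.** The protocol describes one instrument and prints another under the same name. A three-level answer cannot be turned into a five-level one afterwards, because the patient was never offered the intermediate options. On the printed mobility item, every degree of difficulty between none and being bedridden falls into one category.

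This matters because patient-reported benefit is part of the case for the sentinel node procedure. The Summary accepts an additional 5% failure rate on the ground of lower morbidity. Quality of life is one of the secondary outcomes that should show whether patients experience that benefit. A coarser response scale would blunt the comparison, and the response format would not be the one the protocol describes. If the web form followed section 8.1.3 and the paper form followed Appendix 6, answers given in the two modes would also not be on the same scale.

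**Working it through.** No sample-size, power or error-rate formula applies. The check is a count of response options, set against the description.

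**Planned (section 8.1.3).** Five dimensions with five responses each: 5 × 5 = 25 statements. The possible profiles number 5^5 = 3125.

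**Printed (Appendix 6, form headed EQ-5D-5L).** Options in English paraphrase:

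| Dimension | Best | Middle | Worst | Count |
|---|---|---|---|---|
| Mobility | none | some | confined to bed | 3 |
| Self-care | none | some | unable | 3 |
| Usual activities | none | some | unable | 3 |
| Pain/complaints | none | moderate | very severe | 3 |
| Mood | none | moderate | very | 3 |

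Total: 3 + 3 + 3 + 3 + 3 = 15 statements. The possible profiles number 3^5 = 243. The form is 25 − 15 = 10 statements short, two in every dimension.

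**Could lines have been lost when the PDF was read?** This is unlikely. Each dimension shows a complete best, middle and worst option, and there is no gap or missing-figure mark within the list. Accidental loss would hardly remove exactly two levels from all five dimensions.

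**Is it a shortened five-level form?** The wording suggests not. The mobility item passes from "Ik heb enige problemen met lopen" directly to "Ik ben bedlegerig". The middle option is some problems in three dimensions and moderate in the other two. In section 8.1.3, some and moderate are two separate levels within the same scale. The three printed options therefore do not correspond to a fixed subset of the five labels.

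**Which element carries the evidence?** "Ik heb enige problemen met lopen" alone does not prove the fault, since some problems is also one of the five planned labels. The proof is the count, and the fact that "Ik ben bedlegerig" follows as the third and last option.

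**Not counted.** The printed form shows no visual analogue scale. It may have been a figure that was not carried over, so nothing is concluded from its absence.

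**The case against.** The strongest reply is that the appendix may not be what patients see. Under section 8.3 most participants answer through a web link and paper is the fallback. Neither live version is reproduced, so the appendix could be a wrong paste beside a correct survey. This stands, and it makes the consequence conditional on the printed form being used. It does not remove the contradiction, because no other part of the protocol corrects the form.

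Several stronger readings are tempting, but the document does not support them:

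- **That the quality-of-life data are unusable or cannot be scored.** The protocol states no index, value set or scoring algorithm. Section 10.2 speaks only of a linear description and comparison. What is contradicted is the response format, not a scoring plan. Three-level answers used throughout would be coarser, but consistent across groups and visits.
- **That centres will mix versions and create artificial change scores.** Section 8.3 has the questionnaires sent centrally and coordinated by one research nurse. A mismatch between web and paper is possible. Nothing points to a mismatch between centres, or to patients switching version between visits.
- **That lymphoedema symptoms such as heavy legs would be missed.** The adjusted GCLQ in Appendix 6 asks about leg heaviness directly, in the same groups and at the same three time points.
- **That 243 profiles against 3125 measures the damage.** The figures are correct as counts of possible profiles. They measure neither bias nor lost precision, and the protocol gives no basis for either.

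**Conclusion.** The contradiction is certain and lies wholly within the protocol: five levels per dimension in section 8.1.3, and three per dimension on the form printed under EQ-5D-5L in Appendix 6. All five dimensions are affected, with 15 statements against 25.

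The consequence rests on one assumption, that the printed form, or a web form built from it, is the one used. In that case the five-level responses cannot be obtained for the comparison in section 10.2 at any of the three time points in any cohort or group, and the lost intermediate levels cannot be recovered later. If the live forms already have five levels, the error is confined to the appendix. The size of any lost sensitivity cannot be derived from the document.

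The primary endpoint, the sample size and the stopping rule do not depend on this form. The point should be settled because a named secondary endpoint rests on it, but it does not threaten the trial's main conclusion.

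**What to change.** 1. Reconcile section 8.1.3 with Appendix 6. Either replace the printed form with the five-level form that section 8.1.3 describes or, if three levels were intended, rename the instrument and rewrite its description in section 8.1.3 and the Appendix 6 table.
2. Check the live web survey and the paper pack against the corrected appendix and confirm that both offer the same options.
3. If any three-level forms have been completed, record the version for each questionnaire and do not pool those answers with five-level answers as though they were one scale.

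The cost is small: one form exchanged in the appendix (and in the web survey and paper pack if they are also wrong), and a minor amendment. Delay costs more if the three-level form is in use, because each further questionnaire loses response detail for good.

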10.3 Other study parameters

Surgical complications

i.e., incidence of wound infections, wound breakdown, lymph oedema (see adverse effect Appendix 2) per patient and as absolute number. In relation to the previous

history and groin surgery performed, including all surgically treated patients (Groups non SLN cohort and A – C), comparing SLN treated groins with IFL treated groins.

Technical challenges

Description of unintended lesion of vena saphena magna, bleeding etc., duration of surgery to retrieve SLN. In relation to the previous history and groin surgery performed, including all surgically treated patients (Groups non SLN cohort and A – C), comparing SLN treated groins with IFL treated groins.

Patient's preferences

Standard treatment is uni- or bilateral IFL. In this study patients are offered SLN, with IFL when the SLN is not detected or retrieved. Preference for treatment is asked and noted in the file. The treating physician will note patients' preference in the application form. Patients will receive the Decisional Conflict Scale (DCS) and Decision Regret Scale (DRS). questionnaires regarding their treatment choices. (Group A – C) Decisions and regret scales will be compared between the groups (A – C) and related to patient characteristics like age, previous treatment and outcome like tumour positive groins and complications.

USS in follow up (Groups B1 - B2)

- 1) The number of suspicious USS in the follow up of women with negative LKT and SLN: USS with FNA, divided by the number of USS performed *100%.
- 2) Sensitivity and specificity of USS (with FNA) in women with negative LKT and SLN.
- 3) Protocol violation (USS not performed in women with negative LKT and SLN) divided by number of USS required in accordance with protocol *100%.

When a local or regional recurrence is diagnosed FU for this outcome stops.

Additional analyses

For the primary and secondary outcomes (failure of SLN and IFL procedure, feasibility, unexpected nodes, patients preferences, USS) univariate analyses will be done including the following parameters: tumour size, location, infiltration depth, treatment interval 1st and 2nd tumour, previous groin treatment, and age. Variables associated with ($P < 0.20$) in univariate analysis will be included in a multivariate logistic regression model. In the multivariate logistic and cox regression analyses, we only accepted ten events per variable to avoid overfitting (19).

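### Items 5, 7 and 8 of the printed Decision Conflict Scale name a preventive strategy that the trial does not offer; the wording should be matched to SLN and IFL

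*Protocol*

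**What the plan says.** Protocol Appendix 6 prints the form in Dutch. Its introduction reads "De volgende stellingen gaan over de beslissing die u hebt gemaakt over welke operatie u zal ondergaan", that is, the statements concern the decision about which operation the woman will undergo.

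Four consecutive items then ask whether she feels informed about the options:

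- Item 5: advantages, with the wording "voordelen van de innovatieve (nieuwe) preventieve strategie".
- Item 6: "op de hoogte ben van de voordelen van beide opties" (the advantages of both options).
- Item 7: disadvantages "van de huidige standaard preventieve strategie" (of the current standard preventive strategy).
- Item 8: disadvantages "van de innovatieve (nieuwe) preventieve strategie".

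The options themselves are set out in Protocol sections 3 and 5.1. IFL is the standard, the SLN procedure is the alternative whose safety is not yet established, and some women refuse groin surgery altogether. These are groups A, B (split into B1 and B2 by consent to back-up IFL) and C.

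The schedule in Appendix 6 gives the scale to groups A, B1, B2 and C, and section 8.1.3 limits it to baseline. Section 10.3, which covers other study parameters, states "Decisions and regret scales will be compared between the groups (A – C").

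**The concern.** Three items refer to something that is not a choice in this trial. The women already have a first local recurrence and are deciding how the groins are to be treated. No section of the protocol describes IFL, SLN or omission of groin surgery as a preventive strategy. The wording also conflicts with the form's own introduction, which speaks of an operation.

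This is more than a slip in background text, because the form is an instrument that patients read and answer. The scale is given once, and section 8.3 has the participant complete the questionnaires by herself. A misread item therefore cannot be repaired later by an analysis rule. The misreading also need not be equal across groups, and a comparison between groups is what is planned.

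**Working it through.** No sample size, power or error rate depends on this point. The check is a count of items and a comparison of their wording with the options on offer.

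**Structure of the printed form (Appendix 6)**

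- Items 1 to 3: uncertainty about the decision, 3 items.
- Items 4 to 14: contributing factors, 14 − 4 + 1 = 11 items.
- Items 15 to 18: introduced by "Beantwoord de volgende vragen alleen als u de beslissing al heeft gemaakt" (answer only if the decision has already been made), 4 items. The last is "Ik ben tevreden over mijn beslissing".
- Total 3 + 11 + 4 = 18, of which 3 + 11 = 14 are unconditional.

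**Items with the preventive-strategy wording:** 5, 7 and 8.

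- Of all items: 3/18 = 16.7%.
- Of the unconditional items: 3/14 = 21.4%.
- Of the contributing-factor items: 3/11 = 27.3%.
- Of the items asking whether she knows the advantages or disadvantages (5 to 8): 3/4 = 75%.
- Items without the wording (1 to 4, 6, and 9 to 18): 4 + 1 + 10 = 15, and 15/18 = 83.3%.

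**Possible effect on a total score.** The protocol gives no scoring rule, so equal item weights are an assumption. Suppose that, after all items are coded in one direction, the wording moves one group's answers on all three items by one category of the 5-point response scale. The mean item score then moves by 3/18 = 0.17 of a category on 18 items, or 3/14 = 0.21 on 14 items. On a score built from items 5 to 8 alone it moves by 3/4 = 0.75 of a category. The effect on a total is modest; on a knowledge-of-options score it is large. Whether any such shift occurs cannot be known from the protocol.

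**Wording against the options, by group**

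- Groups A and B: the contrast between current standard and new can be read as IFL against SLN, which is how section 5.1 presents the choice. The word for preventive is wrong, but the item can be interpreted.
- Group C: the woman declines both procedures. Items 5, 7 and 8 do not name her choice, and item 6 assumes two options. A woman declining surgery might even take the preventive strategy to mean something else. Items 4, 10 and 11 use open wording (the various options, each option) and do cover her.

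**The case against.** A reader might infer that the three items cannot be answered, and that the total is therefore no measure of the SLN or IFL decision. The protocol does not support either step. The introduction tells the woman that the subject is her operation, and the labels standard and new correspond to the two procedures described to her. Fifteen of 18 items do not contain the wrong term. All three items on uncertainty, the four conditional items and eight of the 11 contributing-factor items are unaffected. That women would guess or skip the three items is a prediction without evidence in the protocol. Since the scoring and missing-item rules may stand in an analysis plan that is not at hand, the total cannot be called uninterpretable.

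Three further objections have weight:

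- **Importance.** The scale is among the other study parameters. Preference is also recorded by the treating physician (section 10.3), and regret has its own five-item scale without this wording.
- **Item 6.** The reference to both options fits the main offer of IFL or SLN. B1 and B2 differ only in consent to back-up IFL. Only group C falls outside it, so a change there is optional.
- **Remedy.** Writing three options into each item would alter the structure of the scale for which section 8.1.3 cites internal consistency of 0.78 to 0.92.

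That the text was carried over from another study is plausible but remains an inference; the point does not need it. What survives is that the wording is wrong on a form given to patients, that it falls on three of the four knowledge items, and that no later analysis can restore the intended answers.

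**Conclusion.** The point holds as a wording defect with limited reach. Items 5, 7 and 8 name a strategy that the trial does not offer and contradict the form's own introduction. They are ambiguous, which weakens the items on knowledge of advantages and disadvantages and any score that includes them when groups A to C are compared. Group C is the most plausible place for a distortion, because neither label describes its choice.

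The affected share is 16.7% of all items, 21.4% of the unconditional ones and 27.3% of the contributing-factor items. Reading these shares as weights in a score assumes equal weighting. The scale is not void. The primary endpoint, the sample size and the stopping rule do not depend on it. Correction is still worthwhile because it is cheap and the baseline answers cannot be collected again.

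**What to change.** In items 5 and 8, replace the phrase for the innovative (new) preventive strategy by the SLN procedure. In item 7, replace the phrase for the current standard preventive strategy by standard IFL. Keep the number and structure of the items.

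Optionally, change the reference to both options in item 6 to wording that also covers no groin surgery, as items 4, 10 and 11 already do.

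If women have already completed the form as printed, record the form version for each participant and report the comparison of groups A to C with a sensitivity analysis that leaves out items 5, 7 and 8.

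The cost is a minor amendment and a text change to one questionnaire. The downside is that answers to those three items cannot be pooled directly across form versions.
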